6.2 Laboratory Procedures/Evaluations

SOURCES OF MATERIALS:

The raw data collected in the current proposal will include MRI and PET scans, blood samples for DNA genotyping, neuropsychological test scores, and clinical data from medical, neurological, psychiatric exams, sleep, cardiologic and respiratory evaluations. Only approved study personnel will interact with participants and have access to subject information. Data will be collected during full-day in-home and nocturnal in-laboratory (polysomnography) sleep studies that are standard clinical practice. Medical records will be kept in accordance with state and federal laws concerning the privacy and confidentiality of medical information. All efforts will be taken to maintain subject confidentiality and research will be conducted following good clinical practices. Each subject will be assigned a unique code number. Confidentiality will be maintained by keeping paper study data in a locked drawer in a locked office. All electronic data will be stored on the Mount Sinai Integrative Sleep Center (MSISC) and NYU Center for Brain Health (CBH) databases such as RedCap, which are password protected and stored within the secure Mount Sinai Medical Center Information Technology (MSMCIT) and NYU Langone Medical Center IT (NYULMCIT) systems. Data will only be available to the key personnel. All have taken HIPAA and IRB tutorials.

6.3 Study Specific Biospecimens

6.3.1 Specimen Collection Procedures

Collection of Blood. We will collect blood at Visit 1 for the baseline and follow-up visits to perform clinical labs and 10 ml of fresh blood to extract DNA (only at the baseline visit) the total amount of blood for both baseline and follow-up visits will be approximately 80cc's. The fresh blood samples will be sent to LGC Genomics where DNA will be extracted and sent back to NYU after GWAS analyses. All data regarding DNA samples will be entered into the ADC-CBH database for sample tracking. While a sample is being processed, one back-up sample with fresh blood will be maintained.

6.3.2 Specimen Preparation, Handling, and Storage

6.3.2.1 Supplies:

-
- 2 PaxGene blood DNA tubes (catalog number 761115)
- 3 purple-topped tubes, 1 red-topped tube, and 2 gold-topped tubes
- 27 Nalgene™ General Long-Term Storage Cryogenic Tubes (Fisher catalog number 5000-0020).

6.3.2.2 General blood handling considerations:

The release of cellular material due to hemolysis into the serum or plasma may introduce additional confounding factors in downstream analysis of such samples. When hemolysis is observed (pink to red tinge in sample that persists after one cycle of centrifuging), this information will be recorded in the plasma/serum (PS) log

6.3.2.3 Serum handling considerations (red topped tubes)

Serum samples should be left at room temperature at least 30 minutes. If the subject is taking any kind of anticoagulant or blood thinner (warfarin, factor Xa inhibitors, heparin, thrombin inhibitors, antiplatelet drugs) (variable name '*anticoag_meds*') at the time of sample collection, leave at least 45 minutes. Check

CONFIDENTIAL

if the clot has formed at 45 and 60 minutes. Record this information in the plasma/serum log (variable 'clot time in minutes'). Steps:

- Check medication list provided by the subject.
- Record any kind of anticoagulant or blood thinner in the PS log
- Record time of blood draw in the PS log.
- Allow blood to clot for a minimum of 30, 40, or 60 minutes in a vertical position at room temperature.
- Observe a dense clot.
- Record time of centrifuge start in the PS log.

6.3.2.4 Plasma Handling Considerations (lavender topped EDTA tubes)

The volume of blood collected in each tube and adequate mixing of the sample into the additive are critical steps.

- Record time of blood draw in the PS log.
- Fill tubes.
- Gently invert tubes 8-10 times.
- Centrifuge at the same time as the serum.

6.3.2.5 Temperature and Light:

Protect samples from extreme temperatures. Transport with icepacks on the sides. Make sure icepacks are never in direct contact with the samples. Do not place blood tubes in windows as direct sunlight can cause the red cells to lyse, and may impact the usability of the specimen.

6.3.2.6 Processing:

- Put 1cc of whole blood from purple tube in two small vial for genetics (vials GEN1-2)
- Heat centrifuge to 21 degrees.
- Spin bloods on at 3000 RPM during 15 minutes.
- Aliquot EDTA plasma into vials PLM1-10. (1.5cc per vial.)
- Aliquot EDTA WBC (buffy coat) into vials WBC1-2. (0.5 cc per vial.)
- Aliquot serum into vials SER1-4. (1.5 cc per vial.)
- Put samples into cryogenic box.
- Transport box to -80C with icepacks on the side.

6.3.3 Specimen Shipment

Specimen Shipment:

Specimens will be shipped on dry ice for DNA extraction and ApoE4 genotyping to LGC Genomics for DNA extraction (LGC, [name]) and NCRAD once a year. Samples will include the 4 digit subject ID only.

6.4 Questionnaire Administration.

All questionnaires are part of the clinical evaluation and are included as addendums

7 Safety and Adverse Events

7.1 Definitions

7.1.1 Unanticipated Problems Involving Risk to Subjects or Others:

Any incident, experience, or outcome that meets all of the following criteria:

- Unexpected in nature, severity, or frequency (i.e. not described in study-related documents such as the IRB-approved protocol or consent form, the investigators brochure, etc.).

CONFIDENTIAL

This material is the property of the NYU School of Medicine and Langone Medical Center. Do not disclose or use except as authorized in writing by the study sponsor

- Related or possibly related to participation in the research (i.e. possibly related means there is a reasonable possibility that the incident experience, or outcome may have been caused by the procedures involved in the research)
- Suggests that the research places subjects or others at greater risk of harm (including physical, psychological, economic, or social harm).

Unanticipated Problems Involving Risk to Subjects or Others

Any incident, experience, or outcome that meets all of the following criteria:

- Unexpected in nature, severity, or frequency (i.e. not described in study-related documents such as the IRB-approved protocol or consent form, the investigators brochure, etc)
- Related or possibly related to participation in the research (i.e. possibly related means there is a reasonable possibility that the incident experience, or outcome may have been caused by the procedures involved in the research)
- Suggests that the research places subjects or others at greater risk of harm (including physical, psychological, economic, or social harm).

Adverse Event

An **adverse event** (AE) is any symptom, sign, illness or experience that develops or worsens in severity during the course of the study. Intercurrent illnesses or injuries should be regarded as adverse events.

Abnormal results of diagnostic procedures are considered to be adverse events if the abnormality:

- results in study withdrawal
- is associated with a serious adverse event
- is associated with clinical signs or symptoms
- leads to additional treatment or to further diagnostic tests
- is considered by the investigator to be of clinical significance

Serious Adverse Event

Adverse events are classified as serious or non-serious. A **serious adverse event** is any AE that is:

- fatal
- life-threatening
- requires or prolongs hospital stay
- results in persistent or significant disability or incapacity
- a congenital anomaly or birth defect
- an important medical event

Important medical events are those that may not be immediately life threatening, but are clearly of major clinical significance. They may jeopardize the subject, and may require intervention to prevent one of the other serious outcomes noted above. For example, drug overdose or abuse, a seizure that did not result in in-patient hospitalization, or intensive treatment of bronchospasm in an emergency department would typically be considered serious.

All adverse events that do not meet any of the criteria for serious should be regarded as **non-serious adverse events**.

Preexisting Condition

A preexisting condition is one that is present at the start of the study. A preexisting condition should be recorded as an adverse event if the frequency, intensity, or the character of the condition worsens during the study period.

General Physical Examination Findings

At screening, any clinically significant abnormality should be recorded as a preexisting condition. At the end of the study, any new clinically significant findings/abnormalities that meet the definition of an adverse event must also be recorded and documented as an adverse event.

CONFIDENTIAL

Post-study Adverse Event

All unresolved adverse events should be followed by the investigator until the events are resolved, the subject is lost to follow-up, or the adverse event is otherwise explained. At the last scheduled visit, the investigator should instruct each subject to report any subsequent event(s) that the subject, or the subject's personal physician, believes might reasonably be related to participation in this study. The investigator should notify the study sponsor of any death or adverse event occurring at any time after a subject has discontinued or terminated study participation that may reasonably be related to this study. The sponsor should also be notified if the investigator should become aware of the development of cancer or of a congenital anomaly in a subsequently conceived offspring of a subject that has participated in this study.

7.2 Recording of Adverse Events

At each contact with the subject, the investigator must seek information on adverse events by specific questioning and, as appropriate, by examination. Information on all adverse events should be recorded immediately in the source document, and also in the appropriate adverse event module of the case report form (CRF). All clearly related signs, symptoms, and abnormal diagnostic procedures results should be recorded in the source document, though should be grouped under one diagnosis.

All adverse events occurring during the study period must be recorded. The clinical course of each event should be followed until resolution, stabilization, or until it has been determined that the study treatment or participation is not the cause. Serious adverse events that are still ongoing at the end of the study period must be followed up to determine the final outcome. Any serious adverse event that occurs after the study period and is considered to be possibly related to study participation should be recorded and reported immediately.

7.3 Reporting of Serious Adverse Events and Unanticipated Problems

For Narrative Reports of Safety Events

If the report is supplied as a narrative, the minimum necessary information to be provided at the time of the initial report includes:

- Study identifier
- Study Center
- Subject number
- A description of the event
- Date of onset
- Current status
- Whether study treatment was discontinued
- The reason why the event is classified as serious
- Investigator assessment of the association between the event and study treatment

7.3.1 Investigator reporting: notifying the IRB

Federal regulations require timely reporting by investigators to their local IRB of unanticipated problems posing risks to subjects or others. The following describes the NYULMC IRB reporting requirements, though Investigators at participating sites are responsible for meeting the specific requirements of their IRB of record.

Report Promptly, but no later than 5 working days:

Researchers are required to submit reports of the following problems promptly but no later than 5 working days from the time the investigator becomes aware of the event:

- **Unanticipated problems including adverse events that are unexpected and related**
 - **Unexpected:** An event is “unexpected” when its specificity and severity are not accurately reflected in the protocol-related documents, such as the IRB-approved research protocol, any applicable investigator brochure, and the current IRB-approved informed consent document and other relevant sources of information, such as product labeling and package inserts.

CONFIDENTIAL

- *Related to the research procedures*: An event is related to the research procedures if in the opinion of the principal investigator or sponsor, the event was more likely than not to be caused by the research procedures.
- *Harmful*: either caused harm to subjects or others, or placed them at increased risk

Other Reportable events:

The following events also require prompt reporting to the IRB, though ***no later than 5 working days***:

- ***Complaint of a research subject*** when the complaint indicates unexpected risks or the complaint cannot be resolved by the research team.
- ***Protocol deviations or violations*** (includes intentional and accidental/unintentional deviations from the IRB approved protocol) for any of the following situations:
 - *one or more participants were placed at increased risk of harm*
 - *the event has the potential to occur again*
 - *the deviation was necessary to protect a subject from immediate harm*
- ***Breach of confidentiality***
- ***Incarceration of a participant*** when the research was not previously approved under Subpart C and the investigator believes it is in the best interest of the subject to remain on the study.
- ***New Information indicating a change to the risks or potential benefits*** of the research, in terms of severity or frequency. (e.g. analysis indicates lower-than-expected response rate or a more severe or frequent side effect; Other research finds arm of study has no therapeutic value; FDA labeling change or withdrawal from market)

Reporting Process

The reportable events noted above will be reported to the IRB using a Reportable New Information submission and will include a description of the event with information regarding its fulfillment of the above criteria, follow-up/resolution, and need for revision to consent form and/or other study documentation. Copies of each report and documentation of IRB notification and receipt will be kept in the Clinical Investigator's study file.

8 Study Oversight

It is the responsibility of the Principal Investigator ([name]) to oversee the safety of the study alongside with the Co-Investigator ([name]). This safety monitoring will include careful assessment and appropriate reporting of AEs as noted above, as well as the construction and implementation of a site data and safety-monitoring plan. Medical monitoring will include a regular assessment of the number and type of serious adverse events.

The PIs will work to develop all aspects of the proposed study including direct oversight, staff supervision, engagement of the Community Advisory Board (CAB), supervision of staff, enrollment and monitoring of eligible participants, acquisition and management of subjective and clinical data, analysis and dissemination of study results. They will also ensure that stated aims are achieved in a timely manner. Moreover, each PI will focus on different but related aspect of the specific aims based on their primary expertise.

CONFIDENTIAL

This material is the property of the NYU School of Medicine and Langone Medical Center. Do not disclose or use except as authorized in writing by the study sponsor

9 Statistical Considerations

9.1 Study Hypotheses

1. Hypothesis 1.1: poor SWS characteristics (short SWS duration, low %SWS, low relative SWA, low SWS continuity and high AI) at baseline will be associated with high %AF. Hypothesis 1.2: psychosocial factors (*e.g.* perceived discrimination) will partially moderate the above relationships.
2. Hypothesis 2.1: race will be associated with longitudinal increases in the annual rate of AD_{PiB}mask change. Hypothesis 2.2: the effect of race in terms of longitudinal increases in AD_{PiB}mask will be partially explained by poor relative SWA at baseline.
3. Hypothesis 3.1: race will be associated with longitudinal changes in global cognition, memory, executive function and sleep-dependent spatial navigational memory. Hypothesis 3.2: the association of race in terms of cognitive decline will be partially explained by poor relative SWA at baseline. Exploratory Hypothesis: absence of improvement in sleep dependent memory consolidation at baseline will be associated with longitudinal decreases in global cognition, memory and executive function.

9.2 Sample Size Determination

Power was assessed under the assumption that dropout replacement will allow complete data to be acquired from 200 subjects. Based on the existing literature²³⁻³², the coefficient of variation (CV) of SWS duration is anticipated to be as high as 90% among AA and 40% among whites. Baseline data from 150 AA and 60 whites will therefore provide 80% power at the 5% significance level to detect a mean SWS duration among whites that is at least 28% higher than among AA. Based on PD4, the CV of PiB uptake at baseline is anticipated to be as high as 35% among AA and 25% among whites, providing 80(90)% power at the 5% significance level to detect a mean PiB uptake among AAs that is at least 13%(15%) higher than in whites. For Aim 1, the study will have 80% power at the 5% significance level to detect correlations of magnitude $|r|=0.20$ (the study from Halder et al³⁹ showed an R^2 of 11, implying an even greater correlation of 0.33 can be expected in our study). The multivariable regression analysis will have 80% power to detect SWS characteristics that can explain 3% of the variance in the longitudinal change in AD_{PiB}mask (Aim 2) or cognition (Aim 3) after adjusting for covariates that together explain at least 25% of the variance in AD_{PiB}mask/cognition. The detectable effect of 3% variance explained, implies the study can detect partial correlations of magnitude 0.1 between SWS and the outcomes adjusted for the cofactors. It is noted that the power of the multivariable analyses will improve if the covariates explain >25% of the variance. The study will have 80% power to detect sleep measures that explain 10% of the variance in the AD_{PiB}mask ratio even if the covariates explain a negligible percentage of the variance.

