2.2 Rationale

Primary Aims. To examine: *i*) whether African Ancestry (%AF) is associated with decreased SWS duration and SWA; *ii*) the effects of race on longitudinal amyloid build-up and its interaction with baseline SWS duration and SWA in cognitively normal elderly; *iii*) the effects of race and its interaction with baseline SWA on longitudinal changes in global cognition, memory, executive function and a spatial navigational memory task. **Exploratory aim.** We will test whether loss of sleep-dependent spatial navigational memory at baseline is a predictor of cognitive decline at follow-up.

Rationale for ethnicity/nativity and clinical groups selection:

Multiethnic cohort studies provide better information about disease causation but they are expensive to design. We will focus on 150 African-American (AA) blacks since African or Caribbean-born are not equally admixed and inclusion of more ethnic groups would result in loss of power for Aim 1 and need for great increases in sample size. As a comparison group, we will include 60 matched non-Hispanic whites. Race will be represented both as binary (self-identified AA vs. self-identified white) and numeric (% of African ancestry). Irregular sleep-wake rhythms and extreme sleep durations may also increase AD risk⁶⁸⁻⁷⁰. The study will not formally test these sleep disorders, as these subjects are hard to recruit in community-based

CONFIDENTIAL

studies (often reluctant to participate in studies that monitor sleep) and the focus is on SWS. Insomnia will be allowed as long as total sleep time (TST) is between 5-9 hours based on actigraphy recordings and sleep logs performed at home.

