9.3 Statistical Methods

General considerations: we will incorporate standard techniques such as omnibus tests and appropriate adjustments to significance (α) levels (*e.g.*, Bonferroni correction) for *post-hoc* contrasts to control for multiple comparisons. Both selection and attrition biases might occur. Appropriate techniques (*e.g.*, Heckman 2-stage approach (GEE Probit Model)^{254;255} and Monte Carlo (EM algorithm)²⁵⁶ will be used to address biases or missing data. Attributes of those who withdrew to follow-up will be contrasted with completers to determine sources of attrition biases. Since only two time points will be analyzed, we will use linear regression models with the annual rate of amyloid change as dependent variable. Significance will be defined by $p < .05$ where p will be Bonferroni corrected when testing *post-hoc* contrasts.

- **Hypothesis (1)**: H1.1) for %AF associations, linear regression models, with each of SWS characteristics as the dependent variable, will be regressed on %AF controlling for age, sex, BMI, AHI, TST, sleep efficiency and WASO. H1.2) This model will test interaction by including the best SWS predictor as dependent variable, the psychosocial factor as a classification factor, %AF and the term created as the cross product of psychosocial factors and %AF.
- **Hypothesis 2-3 (H2-3)**: First we will calculate the associations between race and AD_{PiB}mask represented both as binary (AA *vs.* white) and numeric (%AF). Further analyses will use the representation (s) of race significantly associated with amyloid burden. Second, we will use hierarchical

CONFIDENTIAL

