linear regression, with rate of change of AD_{PiB}mask as the dependent variable and race as independent, adjusting for the matching factors: age, sex, BMI, education and annual income (block 1); ApoE4 and ABCA7 (block 2); DWML volumes, DKI indices and mPFC volume (block 3); and SWS characteristic (*e.g.* relative SWA) (block 4). Other covariates (*e.g.*, psychosocial) will be included in the final models if significantly different between AAs and whites as indicated by unequal variance t tests. Although we anticipate that relative SWA will be the best predictor of longitudinal change in AD_{PiB}mask, the best fitting model will be then replicated with each of the other SWS characteristics not listed before. On a final step, we will test whether the effect of SWS on amyloid deposition is different (*i.e.*, stronger) among AAs. The model would include AD_{PiB}mask change, the binary indicator of race (AA=1 *vs.* white=0) and SWA as described in H1.2. If the interaction is significant, it will imply that the effect of SWA on amyloid varies as a function of race. The sign of the estimated coefficient for this term would indicate whether SWA has a significantly stronger or weaker effect among AA. Exploratory Hypothesis: cognitive z-score change in subjects that show improvement in maze CT will be compared with those that don't show improvement using ANCOVA controlling for age, sex, BMI, race, education and ApoE4 status.

- **Post-hoc analyses**: a subset of *post-hoc* analyses will be performed by controlling by PiB levels at baseline and by splitting the sample into PiB+ and PiB- at baseline and performing a separate analysis for each subset. Stratified analyses will also be performed for men and women, as well as for AAs and whites. In addition, we will formally test the impact of PiB status (defined as PiB SUVR \geq 1.4) on the association of sleep measures with longitudinal increases in AD_{PiB}mask. Although we do not anticipate that sleep or SWS characteristics will change over the follow-up period, *post-hoc* analyses will be performed by assessing longitudinal changes in the sleep measures as correlates and predictors of longitudinal changes in the outcomes measures, using paired sample t-tests to assess the change in outcomes and sleep.

10 Source Documents and Access to Source Data/Documents

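### Does section 9.3 need to name an unequal-variance test for the race and amyloid step, given that section 9.2 powers that contrast with unequal variances?

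*Combined protocol and SAP*

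**What the plan says.** Section 9.2 (Sample Size Determination) sets race-specific variability for baseline PiB uptake: "the CV of PiB uptake at baseline is anticipated to be as high as 35% among AA and 25% among whites". With 150 AA and 60 white participants it claims 80% (90%) "power at the 5% significance level to detect a mean PiB uptake among AAs that is at least 13%(15%) higher" than in whites. It treats slow wave sleep (SWS) duration the same way: "the coefficient of variation (CV) of SWS duration is anticipated to be as high as 90% among AA and 40% among whites". Neither sentence states whether the test is one- or two-sided.

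Section 9.3 (Statistical Methods) opens Hypotheses 2-3 with "First we will calculate the associations between race and" the amyloid index (AD_PiBmask), with race coded as binary and as percentage African ancestry (%AF). It continues: "Further analyses will use the representation (s) of race significantly associated with amyloid burden". The threshold is p < .05. No test, covariate set or standard error is given for this step.

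Two other statements in 9.3 bear on it. The general considerations say "we will use linear regression models with the annual rate of amyloid change as dependent variable". Further covariates enter the final models "if significantly different between AAs and whites as indicated by unequal variance t tests".

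**The concern.** The sample size section assumes unequal variances, and the methods section does not carry that assumption into the contrast it was made for. Linear regression is the only model 9.3 names for amyloid. Its default standard error for a binary predictor without covariates is the pooled one. Here the larger group is also the more variable, so pooling overstates the standard error and costs power.

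The step also acts as a gate: its result selects the race variable or variables for the hierarchical models behind H2.1 and H2.2. If it were run with less power than 9.2 promises, a real difference could be missed more often than planned, and the choice of standard error would be left to the analyst at a selection step driven by significance.

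**Working it through.** **Inputs (section 9.2).** AA n = 150, CV up to 0.35; white n = 60, CV up to 0.25; 5% level, taken as two-sided. Set the white mean to 1 and the AA mean to 1 + d. The SDs are then 0.25 and 0.35(1 + d). Normal approximation; Φ is the standard normal distribution function.

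**Formulas.**
- True standard error: SE = √(0.25²/60 + SD_AA²/150)
- Pooled standard error: SEp = √[(149·SD_AA² + 59·0.25²)/208] × √(1/150 + 1/60)
- Power, unequal-variance test: Φ(d/SE − 1.96)
- Power, pooled test: Φ((d − 1.96·SEp)/SE)

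**The plan's own figures.**
- d = 0.13: SD_AA = 0.3955, SE = 0.0457. Power = Φ(2.847 − 1.96) = 81%, against 80% stated.
- d = 0.15: SD_AA = 0.4025, SE = 0.0461. Power = Φ(3.257 − 1.96) = 90%, against 90% stated.
- SWS duration, AA mean 1, white mean 1.28, CVs 0.90 and 0.40: SE = √(0.512²/60 + 0.9²/150) = 0.0988. Power = Φ(0.28/0.0988 − 1.96) = 81%, against 80% stated.

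All three reproduce. The method is not pinned down uniquely: a one-sided pooled test gives 81% and 90% for PiB and 78% for SWS.

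**The feared case: unadjusted, two-sided, pooled, CVs at their ceiling.**
- d = 0.13: SEp = 0.0550, ratio SEp/SE = 1.21. Power = Φ(0.485) = 69%.
- d = 0.15: SEp = 0.0559, ratio 1.21. Power = Φ(0.879) = 81%.
- No race difference: SE = 0.0431, SEp = 0.0496. False-positive rate = 2 × [1 − Φ(1.96 × 0.0496/0.0431)] = 2.4%.

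A simulation of 200,000 normal data sets agrees: pooled 68% and 81%, Welch 81% and 90%, with null rejection rates of 2.4% and 4.9%.

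**How quickly the shortfall goes away.** The covariate rows assume the covariates explain the same share of variance in both groups and are unrelated to race, so both standard errors are multiplied by √(1 − R²). The 25% is the figure 9.2 gives for the longitudinal-change models, borrowed here as an assumption. The 10% is also an assumption.

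| AA CV | R² | Pooled, 13% | Pooled, 15% | Unequal-variance, 13% | Unequal-variance, 15% |
|---|---|---|---|---|---|
| 0.35 | 0 | 69% | 81% | 81% | 90% |
| 0.35 | 0.10 | 74% | 85% | 85% | 93% |
| 0.35 | 0.25 | 82% | 92% | 91% | 96% |
| 0.30 | 0 | 80% | 90% | 86% | 94% |
| 0.25 | 0 | 89% | 95% | 91% | 96% |

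At an AA CV of 0.30, or at 0.35 with R² of 0.25, even the pooled test delivers roughly the stated 80% and 90% or better.

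**The case for a change.** The strongest case for a change is that the remedy is cheap and the gap is real. One sentence would tie the test in 9.3 to the assumption in 9.2. The authors clearly knew the unequal-variance test, since they assign it to covariate screening, yet they did not assign it to the contrast they powered that way. Settling the standard error in advance would also remove discretion at a step that selects variables by significance.

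That much stands: the test is not named. The harm is less secure.

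- The loss needs ordinary regression, default standard errors and no covariates, all together. The plan asks for no such combination. An analyst making a plain two-group comparison finds only one such AA versus white test named in 9.3, and it allows unequal variances. An analyst who follows the regression models for H1.1 or for rate of change finds models with covariates.
- Reading the step as baseline is an inference. It rests on the phrase about amyloid burden, on the contrast with rate of change in the second step, and on 9.2. If the step uses change instead, the documents give no race-specific variances and the calculation does not apply.
- The plan does not say what follows if neither representation is significant. Race remains the independent variable in the hierarchical model, and the final interaction step uses binary race regardless. A miss here therefore cannot be traced to the loss of a stated test.
- How often both representations would miss together can be estimated only by assuming a distribution of African ancestry, which the documents do not give.

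**Conclusion.** No change to the plan follows. Section 9.2's power figures are correct under two-sided unequal-variance testing, and 9.3 contains no rule that contradicts them. It leaves one screening step without a named test, a gap an analyst would probably fill in keeping with 9.2.

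The worst case is a fall from 81% to 69% power at a 13% difference and from 90% to 81% at 15%. It requires an unadjusted, two-sided, equal-variance test and an AA CV at the 35% ceiling with the white CV at 25%. It also assumes approximately normal data and the baseline reading of the step. The error would be conservative (about 2.4% false positives instead of 5%), and most or all of the shortfall against the stated power disappears with an AA CV of 30% or with covariates explaining a quarter of the variance.
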